### **12.2.2 Data security, access and back-up**

The server hosting the Smart Trial EDC system and the database is kept in a locked server-room in Denmark. Only the system administrators have direct access to the server. A role concept with personal passwords (site investigator, statistician, monitor, administrator etc.) regulates permission for each user to use the system and database as he/she requires.

To enter data, a two-step verification system is used in addition to a permission-based access control with varying levels of access depending on the person's role within the trial. All data entered into the CRFs are transferred to the database using Secure Sockets Layer (SSL) encryption. Each data point has attributes attached to it identifying the user who entered it with the exact time and date. Retrospective alterations of data in the database are recorded in an audit table. Time, table, data field, original value and altered value, and the person are recorded (audit trail).

A multi-level back-up system is implemented. Back-ups of the whole system including the database are run several times per day. The back-up-data are stored in a secure place on a different storage-server.

### **12.2.3 Analysis and archiving**

At final analysis, data files will be extracted from the database into statistical packages to be analysed. The data will remain anonymised during and after the statistical analysis. The database will be locked at this time, recorded in special archiving format and securely stored for at least 1 year. In addition, the PI will receive a USB flash drive of the trial data for archiving at the site.

### **12.2.4 Electronic and central data validation**

Data can be entered into the database only after a check of completeness and plausibility. Additionally, the statistician creates the eCRFs with restrictions on data points that only allow expected number ranges, and furthermore, selected data points are cross-checked for plausibility with previously entered data for that participant.

Monitoring is used to validate entries with source data

### **12.3 Monitoring**

The study site will be monitored by an employee of the Sponsor. A minimum of 3 visits will be performed; one site initiation visit, 1 routine monitoring visits, and one close out visit. The number of routine monitoring visits will be increased if needed based on the course of the study. The first routine monitoring visit will take place shortly after at least 5 patients have been enrolled.

Source documents will be made available for the monitor and the principle investigator or a delegated and authorized person will be available during the visits to answer questions.

100% source data verification will be completed for 3 patients at the first interim visit. For any additional interim visits, another 3 patients of 100% source data verification will be completed at each visit.

Subject to SDV for all patients are: Patient Informed Consent Form Eligibility criteria

Diagnosis Visit dates

Study intervention details related to: Procedural success

Procedure date and time

(Serious) Adverse Events Device deficiencies

The content of Investigator Site File (ISF) will be checked during each monitoring visit.

### **12.4 Audits and Inspections**

CEC has the right to execute inspections at the study site. The Sponsor may at any time conduct an audit of the study site.

The study documentation and the source data/documents must be made accessible to auditors/inspectors and questions have to be answered during audits/inspections. All involved parties must keep the participant data strictly confidential.

### **12.5 Confidentiality, Data Protection**

Direct access to source documents will be permitted for purposes of monitoring (12.3), audits and inspections (12.4) (ICHE6, 6.10) and only authorized persons involved in those activities will have access to source documents and must keep participants data strictly confidential. Only those involved with the trial (PI, statistician, monitor) will have access to the protocol, dataset, statistical code, etc. during the study and after the study the information will be made public through a publication of the results; however, trial participants' identities will remain coded.

### **12.6 Storage of biological material and related health data**

No biological samples are taken or stored. Data collected during the trial will be stored and potentially reused for further analysis only with the participants' consent independent of the study. The data will remain encoded because results are only recorded using the identification code of the subject.

## 13. PUBLICATION AND DISSEMINATION POLICY

Trial results will be communicated to participants at the end of the trial. The trial results primary purpose is for internal product validation to ensure safety and performance of the device. The results will be communicated to other relevant groups (e.g., via publication, reporting in results databases, and other internal data sharing arrangements) as needed and for the purpose of sharing scientific information within the industry. The only people with authorship eligibility will be those that worked on the trial including the PI, statistician, and the monitor involved in testing. Any plans for writing will not include access to the full protocol but a description of it as well as a description of the participants. Statistics will be described sufficiently so that the reader understands the analysis and any conclusions made from it. Ultimately the decision to submit the report for publication and the ultimate authority over any of the activities is held by the Sponsor, Bernafon.

## 14. FUNDING AND SUPPORT

### 14.1 Funding

The Sponsor will financially support the trial including providing the clinic and all materials needed to complete the testing. This includes the devices themselves as well as equipment.

## 15. INSURANCE

Insurance will be provided by the Sponsor. A copy of the certificate is filed in each investigator site file and the trial master file.

## **17. APPENDICES**

1. Medical Devices: IB (according to ISO 14155)
2. Medical Devices: Declaration of Conformity
3. Case Report Form (e.g.) CRF
4. Instructions for Use
5. Statistical Plan
6. Patient Information and Informed Consent
7. List of study sites/PI
8. Questionnaires

1.2 SAP and protocol version

Date	SAP Version	CIP Version	Identification	Comment
2019.07.22	1.0	1.0	[name]	Document created

2. INTRODUCTION

The study protocol includes an outline of the statistical methods to be employed in the analysis of the data. The purpose of the Statistical Analysis Plan is to provide full details of the planned statistical methods to be used in the primary report of the trial results. It has been produced in line with the ICH E9 Guidelines and guidelines from Gamble et al. (2017).

2.1 Background and Rationale

Amplification and signal processing within hearing aids are designed to mainly improve speech understanding. It is possible to model the acoustical characteristics of speech because they are defined by the human vocal tract characteristics and the articulation speed. This acoustical model of speech is then used as a guideline for optimizing signal processing within the hearing aid.

This approach has shown limitations in terms of perceived sound quality when listening to recorded or live music (Madsen et al., 2015; Looi et al., 2019). Kirchberger & Russo (2016) suggest that the characteristics of music shows more variations than speech in terms of frequency range, sound level, modulation, and dynamic range. The consequence of this larger variability is that no universal model can be used to define a music signal, which, in turn, makes it difficult to define the amplification and signal processing needed for a music program (Greasley et al., 2019). While music already presents a challenge for listeners wearing hearing aids, the challenge might be even more complex for musicians. Vaisberg et al. (2018) highlight that hearing-impaired instrumentalists face challenges in their music activities while wearing hearing aids because there is often little knowledge about individual music practice (music style, instrument range, etc.) or their expectations of music amplification.

The specific topic of hearing aid settings optimized for musicians has not received, to our knowledge, much attention from the research community. Many papers evaluate the effect of hearing loss and music or the effect of hearing aid settings for listening to music, but their design doesn't specifically target hearing-impaired musicians (Mussoi & Bentler, 2015), or the target population for studies is mixed, e.g. with or without musical training, (Kirchberger, 2015). In general, the test design of these trials concentrates on listening to music only, not playing. A single publication, with a focus on hearing aid use while musicians are playing (Vaisberg et al., 2018), supports the need to improve and individualize the fitting of hearing aids for musicians.

The need to optimize the music program is also motivated by:

- The prevalence of hearing loss and associated audiological symptoms among musicians exposed to high sound levels (Di Stadio et al., 2018). This target population could benefit from hearing aids that don't restrict their abilities to play music,
- The benefit (social, cognitive, and physical) of playing music especially for hearing impaired (Leek et al. 2008) and seniors (Lehmberg & Fung, 2010). Music is a multi-sensorial activity which reinforces social and communication skills (Fulford & Ginsborg, 2014). It is therefore important to allow hearing-impaired musicians to continue their musical activities.

2.2 Objective and hypothesis

The assumption is that hearing aids that are optimized for hearing-impaired musicians should provide a better experience while playing an instrument with the following consequences: (a) improvement of the perception of music, (b) improvement of the ability to play, and (c) indirect improvement of the quality of life.

The results of the trial will be used to examine the benefit provided by the fitting protocol optimized for hearing-impaired musician (Greasley et al., 2019) compared to the standard fitting approach, as well as identify further optimization of the tested products. In summary, the primary reason for this study is to evaluate the new fitting protocol for musicians using hearing aids. The secondary reason is to evaluate the overall safety of the IMD by testing for unexpected behaviour from the IMD and by the collection of AEs to identify any new risk factors since their release to the market as a post-market quality control.

More specifically, the objective of the trial is to provide answers to following research questions:

- Does the fitting protocol optimized for hearing-impaired musician's individual needs make an audible difference compared to a standard fitting approach?
- Is the fitting protocol optimized for hearing-impaired musician's individual needs preferred over the standard fitting approach?
- Does the fitting protocol optimized for hearing-impaired musician's individual needs improve the perception of music compared to a standard fitting approach?

3. STUDY METHODS

3.1 General study design and plan

Bernafon AG will carry out testing with musicians who have a hearing loss within the fitting range of the investigational medical device (IMD) in order to validate the performance of the fitting protocol optimized for musicians. The intended purpose of the study is to compare the performance of two different music programs within the IMD which is currently sold on the market. The programs will be referred to as the Investigational Protocol (IP), i.e. a program individually optimized for each participant with his own instrument, and the Standard Protocol (SP), i.e. the default music program provided by the IMD, throughout this document.

For the current study, the IMD is a miniRITE (MNR) behind-the-ear (BTE) style which offers the possibility to the user to select different listening programs. Hearing aid acceptance and overall benefit will first be evaluated using a single general program, fitted during the first visit with a NAL-NL2 fitting rationale (not music specific). The first field period will take place after the first visit and should also ensure that there are no comfort or manipulation difficulties when the participants are using the hearing aids. Musical experiences will be evaluated with the general program during the first visit and the first field test to get the baseline performance of music amplification. The fitting rationale used for the first field test is not designed for music, therefore two additional programs specifically designed for music will be programmed during the second visit and tested during the second field test. One music program

will use the standard protocol (SP) for live music and the other program will use the investigational protocol (IP) (an optimized method for music performance). Each program is accessible via a local control on the IMD housing. Data from the first field test will be used as reference for each subject and data from second field test will be collected to answer the research questions.

A randomised and single-blinded, single-arm design will be used for the field tests, and the lab test order will be randomized and single-blinded. The performance of the different amplification strategies will be evaluated in a controlled environment using a music perception test and during the field test using questionnaires. This approach should cover the range of use cases to better understand the effect of the IP over the SP.

The current trial is a pilot / explorative test because no publication can be directly used for the methodology, sample size calculation, or data analysis. However, cited publications with a relation to the topic (e.g. perception of music, music and hearing aids, music and hearing-impaired listeners, etc) will serve as reference for the trial set-up.

3.2 Randomization

The study is based on repeated measures with the SP and the IP. Participants are asked to switch between the listening programs in a given condition (practice, rehearsal, or concert) in order for them to gather comparable experiences while playing and listening to music.

Program allocation effect, i.e. higher likelihood to use program 2 than 3, will be compensated by randomizing the order of the tested protocols in the listening program slot. This risk is outbalanced by the benefit of directly comparing the same listening situation with both programs.

The program order will be randomized, and the lab test order will follow the program order randomization. The active participation of the investigator is required for the IP resulting in a single blind (participant only) design. The randomization list will be provided to the investigator by the statistician and documented before the recruitment process starts.

The randomization list will be generated with a random permuted block method and a random digit link to control any potential order inequality. Pocock (1983, p 77) provides a link between random digits and the structure of blocks for four patients and 2 treatments (order). No stratification is foreseen because no confounding factors have been identified at this stage of the study design.

3.3 Sample Size

Vaisberg et al. (2018) is the only publication, to our knowledge, specifically focusing on hearing aids for hearing impaired musicians. They used a qualitative research methodology based on semi-structured interviews with 12 participants. Fullford et al. (2011) and Fullford & Ginsborg (2014) also used 12 participants for qualitative research studies about how hearing-impaired musicians experience sound and communicate while playing music. However, these publications are based on qualitative research methods which cannot be directly used for the sample size estimation.

The list below summarizes the sample sizes and population attributes from quantitative research tests in a lab, i.e. exclusion of questionnaire-based research, with a topic related to the current study:

- Croghan et al. (2014) investigated the preference of signal processing within hearing aids while listening to music with 18 hearing aid users with paired comparisons. Sub-group analysis was made based on the music experience, i.e. 9 listeners in the musician group and 9 listeners in the non-musician group.
- Kirchberger & Russo (2015) compared music perception with the adaptive perception test in the unaided condition with 21 hearing impaired and 19 normal hearing listeners. However, music experience showed great variation among the participants.
- Prentiss et al. (2015) evaluated chord discrimination and timbre perception with listeners presenting the following characteristics: normal hearing, hearing aid user, bi-modal hearing (hearing aid and cochlear implant), and cochlear implants. Each subgroup was composed of 14 participants without indication about their musical activities.
- Mussoi & Bentler (2015) evaluated the effect of a specific signal processing algorithm (frequency lowering) on the sound quality while listening to music using paired comparisons. They recruited 30 normal hearing listeners (15 with and 15 without musical training) and 27 hearing impaired listeners (15 without and 12 with musical training).
- Kirchberger & Russo (2016) evaluated the effect of another signal processing algorithm (dynamic range compression) using the adaptive music perception test. They recruited 31 hearing aid users with varying musical experience (from none to professional musician). From the overall sample, only 14 participants had a positive score regarding their musical experience.

The sample size ranges between 9 and 21 participants when looking at hearing aid users with a certain amount of musical training. This range can be used as a baseline for the sample size definition. However, there are some known limitations when using these references. Their study designs only include tests where the participants listen to predefined music samples and not when they are playing their own musical instruments. The definition of the sample size for this exploratory trial should take the population homogeneity and the recruitment potential into account.

On one hand, arguments for a sample size closer to the lower boundary might be justified by a relative homogeneous population reflecting a strong external validity potential because:

- The hearing loss is within the fitting ranges of the IMD, i.e. exclusion of participants with a too mild or profound hearing loss degree,
- The musical experience and practice are set as inclusion criteria, i.e. participants are regularly playing an instrument in different groups or ensembles,
- The recruitment process is restrictive. The target population must fulfil the inclusion / exclusion criteria and be ready to bring their own instrument for the IP fitting. These criteria will eliminate potential participants with cognitive, social, or physical limitations.

On the other hand, there are some unknown parameters that have also to be considered for the sample size definition:

- The effect of the instrument, i.e. the sound generation principle greatly varies between a string, a woodwind and a brass instrument. This might affect the perception of sound and

interact with the range of the instrument, the hearing loss degree and type,

- The effect of amplification through hearing aids when musicians are playing. All the above-mentioned tests are based on passive listening experience. There are no publications, to the best of our knowledge, about the use of auditory feedback to control the production of music. We can assume that adaptation of their own voice production to the environment (Lombard effect) and perception of sound might show similarities when playing music,
- The effect of the IP which follows guidelines for hearing aids fitted to musicians. The guidelines are based on a project (Greasley et al., 2019) but no results based on quantitative research were published. It is therefore not possible to estimate an effect size when a personalized protocol like the IP is used with musicians.

The uncertainty from the test design and the unknown effect size from the IP motivates the choice for a larger sample size. Regarding recruitment possibilities, based on the principal investigator's input, the sample size was set to 18-20 participants for the current study.

3.4 Timing of data analysis

Independent study monitoring will be conducted in adherence to the Good Clinical Practice guidelines before the data are downloaded and transmitted to the statistician. Data cleansing and validation will be performed upon completion of the last visit of the last patient included in the study. The final analysis will be conducted thereafter. Based on the trial design and the risk evaluation, no motivation was identified to conduct an interim analysis.

4. STATISTICAL PRINCIPLES

4.1 Levels of confidence intervals and p-values

Inferential statistical tests will be performed using the two-sided $\alpha = 0.05$. All reported p-values greater than or equal to 0.001 will be rounded to three decimal places and p-values less than 0.001 will be displayed as " <0.001 ". Confidence intervals are computed from observed data at 95%.

4.2 Analysis populations

The analysis of the primary outcome will be based on the intention-to-treat (ITT). The ITT population will include all participants with associated primary outcome data, excluding only subjects who were deemed ineligible following screening visit, those who withdrew from the trial, were unwilling for their previously collected data to be utilised or those who failed to provide baseline.

5. TRIAL POPULATION

The following demographic and baseline characteristics will be tabulated overall for the ITT and per protocol population: Age (years), Gender (categorical variable), Hearing Loss Degree (from/to categories), 4-frequency Pure Tone Average (in dB HL), Acoustical Coupling with the IMD (categorical variable), music experience, and history, i.e. hearing loss onset, ear surgery, otalgia, otorrhea, otitis, tinnitus, and noise exposure.

For continuous variables (e.g. age), descriptive statistics will be presented (mean, standard deviation, median, minimum, maximum, interquartile range and number of participants with data). For categorical variables, the data will be presented using percentages, frequency and number of participants with data. The denominator for the percentages will be the number of patients with non-missing data.

6. ANALYSIS

6.1 Outcome definitions

6.1.1 Primary Objective

The study will assess the performance of the IP in comparison to the SP using a preference questionnaire. After wearing the devices for at least 10 +/- 7 days and using them in daily life and various music situations, the subjects will be asked to complete a preference questionnaire and choose between the two music programs (SP and IP).

6.1.2 Primary Outcome Measure

The primary outcome is measured with a preference questionnaire in which the subjects must choose which program (IP or SP) they preferred for listening and playing music. They must also state how sure they are of their decision and indicate from a list of qualities upon which their decision is based.

6.1.3 Secondary Objectives

The secondary objective is to assess the perception of music with the IP in comparison to the SP using the adaptive music perception (AMP) test (Kirchberger & Russo, 2015). The AMP provides a means to evaluate perception of details in music with various subscales, e.g. pitch, duration, loudness. The hypothesis is that the performance of the IP should not be inferior to that of the SP. Baseline scores for the AMP test are measured unaided and aided with the general listening program, i.e. not specific for music.

Additionally, a music perception questionnaire based on Rutledge (2009) will evaluate the perception of music in various environments with each listening program. Overall hearing aid benefit will be measured with a general product questionnaire

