musical setup). For musicians the dedicated program may require further optimization and fine-tuning specific to their instrument and/or the situations in which they play music.

For this study, Bernafon AG will carry out testing with participants that are musicians with hearing loss to compare dedicated music programs. The current study will compare the standard music program available in the software to one that is fine-tuned for each participant. The Bernafon hearing aids used for the current study are CE- marked and have been on the market for almost one year. The goal is to determine whether musicians will perceive a difference and prefer a fine-tuned music program over the default music program in real-life situations.

The devices used for the trial are the Bernafon Viron 9 miniRITE (MNR) behind-the-ear (BTE) hearing aids. The results of the trial will be used to examine differences in the benefit provided by the two music programs as well as identify further optimization possibilities of the default music program provided by the fitting software. Objective measures will be made with Real Ear Measures (REM) to verify the output of the hearing aids, and subjective differences will be measured with questionnaires and an adaptive music perception test (Kirchberger & Russo, 2015).

All participants are hearing impaired persons that play an instrument. The trial will consist of a total 3 appointments. For the field testing and the lab testing, the order of the programs (optimized or default) will be randomized. It is expected that the optimized program will perform better than the default program for perception and preference testing.

In summary, the primary goal of this study is to evaluate the currently marketed hearing aids regarding their performance with music and to further validate the safety of the devices.

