### **4.3 Secondary Objectives**

The secondary objective is to assess the benefit of the IP in comparison to the SP using an adaptive music perception test. The performance of the IP should not be inferior to that of the SP. Additionally, questionnaires will be used to control for a general acceptance of the hearing aids, sound quality of music, and to monitor for unexpected device behaviour.

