#### **8.1.1 Experimental Intervention (medical device)**

The investigational product (IMD) is a medical device. It is the current version of the marketed Bernafon hearing device. The name is Viron 9. It was released to the market in early 2019. One BTE hardware style will be used for the trial. It is called a BTE miniRITE (MNR) and is appropriate for mild to profound hearing losses (depending on the speaker that is used). The device uses a disposable battery that lasts for approximately 5-7 days of use.

The BTE MNR is fitted with the body of the device over the ear, and the speaker covered with a dome or earmold inside of the ear canal. The performance of the IP is expected to be the same or better than the SP. They are non-invasive devices. The dome that is worn inside the ear canal is made from non-toxic plastic and the earmolds are made of non-toxic plastic with an acrylic coating. An illustration of the IMD is shown in Figure 1.

Figure 1. Viron 9 miniRITE

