#### **11.4.3 Secondary Analyses**

The secondary objective is to assess the perception of music with the IP in comparison to the SP using the adaptive music perception (AMP) test (Kirchberger & Russo, 2015). The AMP provides a means to

evaluate perception of details in music with various subscales, e.g. pitch, duration, loudness. The hypothesis is that the performance of the IP should not be inferior to that of the SP. Baseline scores for the AMP test are measured unaided and aided with the general listening program, i.e. not specific for music.

The AMP test is based on an adaptive procedure that provides the threshold reflecting the amount (time, loudness, pitch...) that each participant can detect above chance. The thresholds are measured on ratio scales: duration in milliseconds, pitch in hertz, loudness in decibels. Kirchberger & Russo (2015) indicate that the thresholds might be influenced by different covariates, like degree of hearing loss or music experience, and by the type of signal processing. Measured thresholds will therefore be modelled by a linear mixed-effect regression with backwards selection based on the variation inflation factor (VIF). This gives a complex picture for the coefficient interpretation as there are 4 test conditions: unaided, aided general program, aided SP, and aided IP. Planned contrasts will be considered:

1. Unaided vs Aided
2. General vs Music-specific programs
3. IP vs SP

The 3rd research question will be answered with a paired t-test on each subscale comparing threshold from the IP to the thresholds from the SP.

Additionally, a music perception questionnaire based on Rutledge (2009) will evaluate the perception of music in various environments with each listening program. Overall hearing aid benefit will be measured with a general product questionnaire

The results from the music questionnaire are scores from a visual analogue scale. The distribution of the scores will be visualized with boxplots for each listening program (General, IP, or SP program) and focus (own musical instrument vs other musical instruments). The effect of listening programs and focus will be evaluated with mixed effect regression model taking into account the hearing loss degree, own instrument category (string, woodwind, or brass), and music experience as fixed effects. Planned contrasts will be considered:

1. General vs Music-specific programs
2. IP vs SP

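### The AMP hypothesis is worded as non-inferiority, but with no margin or confidence-limit rule the planned difference tests cannot support it when the result is non-significant

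*SAP*

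**What the plan says.** **The hypothesis.** Protocol 4.3 says of the AMP comparison: "The performance of the IP should not be inferior to that of the SP". Protocol 11.4.3 and SAP 6.1.3 repeat this and label it the hypothesis for the outcome: "The hypothesis is that the performance of the IP should not be inferior to that of the SP".

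**The expectation and the research question.** Protocol 3.1 goes further: "It is expected that the optimized program will perform better than the default program for perception and preference testing". Protocol 8.1.1 is more cautious: "The performance of the IP is expected to be the same or better than the SP". Research question 3 (protocol 11.1, SAP 2.2) asks whether the protocol optimized for the musician's "individual needs improve the perception of music compared to a standard fitting approach".

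**The analysis.** Protocol 11.4.3 and SAP 6.2.2 plan two IP-SP comparisons on the AMP: the third contrast of a linear mixed model, and a paired t-test on each subscale. The t-test is assigned to research question 3. SAP 4.1 sets the level: "Inferential statistical tests will be performed using the two-sided" 0.05. It adds: "Confidence intervals are computed from observed data at 95" per cent. Neither document states a non-inferiority margin or links a confidence limit to a conclusion.

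**The concern.** A non-inferiority hypothesis needs a stated largest acceptable deficit and a rule, normally that a confidence limit excludes that deficit. A two-sided difference test has neither. Three outcomes are possible on the AMP:

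- The interval lies wholly on the side favouring the IP. This supports *not inferior*, and also improvement.
- The interval lies wholly on the side favouring the SP. This counts against *not inferior*.
- The interval spans zero. The plan then gives no way to judge its own hypothesis.

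The third outcome is the problem. The hypothesis as worded invites p>0.05 to be read as showing that the IP is no worse, and nothing in either document rules that reading out. At stake is what may be concluded about music perception from the AMP.

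**Working it through.** **No planned figure to reproduce.** The sample size of 18-20 was set from the range of earlier studies (9 to 21) and recruitment possibilities (protocol 11.2, SAP 3.3). No power, effect size, SD or margin lies behind it, and SAP 3.3 says an effect size cannot be estimated. The check therefore asks what the planned test can show at that size.

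**Inputs**
- n = 18 or 20 complete pairs. SAP 6.3 plans no imputation, so missing pairs would make the figures worse.
- Two-sided alpha 0.05 (SAP 4.1).
- d = true mean IP-SP difference divided by the SD of the paired differences. All values of d are assumptions.

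**Step 1: width of the 95% confidence interval.** Half-width in SDs of the paired difference = t(0.975, n-1)/√n.
- n = 18: 2.110/4.243 = 0.497
- n = 20: 2.093/4.472 = 0.468

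So even if the observed difference were exactly zero, the interval would still include an IP deficit of almost half an SD.

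**Step 2: chance of a non-significant result.** With t* = t(0.975, n-1) and F the noncentral t distribution function with n-1 degrees of freedom and noncentrality d√n:

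P(p>0.05) = F(t*) - F(-t*)

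| Assumed size of d | n = 18 | n = 20 |
|---|---|---|
| 0 | 95% | 95% |
| 0.2 | 87% | 86% |
| 0.3 | 78% | 75% |
| 0.5 | 48% | 44% |
| 0.8 | 11% | 8% |

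The result depends only on the size of d, not its sign. An IP worse by 0.3 SD and an IP better by 0.3 SD give p>0.05 equally often, so p>0.05 cannot tell them apart.

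**Step 3: where non-significance becomes the more likely result.** Solving P(p>0.05) = 0.5 gives d = 0.490 for n = 18 and 0.462 for n = 20.

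**Step 4: could a margin be added instead?** If the programs are truly equal, a rule that the 95% limit must exclude the margin has this power:

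| Assumed margin (SD of the paired difference) | n = 18 | n = 20 |
|---|---|---|
| 0.3 | 22% | 25% |
| 0.5 | 52% | 56% |
| 0.7 | 80% | 84% |

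For 80% power, the exact t calculation needs about 90 participants for a margin of 0.3 SD and 34 for 0.5 SD.

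**The case against.** The best defence is that the paired t-test is assigned to research question 3, and a two-sided difference test suits an improvement question. *Better* implies *not inferior*, so the passages do not contradict each other. The non-inferiority sentence can be read as a loose expectation, like the one in protocol 8.1.1. The planned 95% intervals would show how large an IP deficit remains compatible with the data. The trial is labelled exploratory and the AMP is secondary.

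Most of this stands, and it limits the weight of the point. It does not rescue the sentence. Protocol 11.4.3 and SAP 6.1.3 call it the hypothesis for this outcome; if the t-test belongs only to research question 3, that hypothesis has no valid test. The intervals would carry the information, but no rule connects them to it.

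Stronger readings are tempting and are not supported:

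- *The sponsor plans to declare non-inferiority from a null result.* No text says so. The wording leaves the reading open.
- *A null AMP result is to be expected.* That holds only for true differences below about 0.46 to 0.49 SD, and the documents give no effect size. At 0.8 SD the test would be significant about 89% to 92% of the time.
- *The AMP score is undefined.* Protocol 9.2.2 defines the score of an adaptive run from its last four reversals. SAP 6.1.4 names two subscales, meter and timbre, with three dimensions each, whereas SAP 6.1.3 gives pitch, duration and loudness as subscales. No rule for combining dimensions is written here, but the cited test publication may supply one. This is a point of clarity.
- *A definite false-positive rate attaches to research question 3.* The number of AMP and questionnaire tests is not fixed by the documents, so no such figure can be derived.

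**Conclusion.** The point holds, and is worth correcting before the data are analysed. The plan states a hypothesis that its own analysis cannot support when the interval spans zero. The half-width is about 0.5 SD of the paired difference at n = 18-20, and an IP truly worse by 0.3 SD would escape detection about 75% to 78% of the time. The half-width follows from n and the confidence level alone. The 75% to 78% rests on the assumed 0.3 SD deficit, complete pairs and the paired t-test model.

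A significant result in favour of the IP would still support the hypothesis. The consequence is confined to the conclusion drawn from an exploratory secondary outcome.

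**What to change.** 1. In protocol 4.3, protocol 11.4.3 and SAP 6.1.3, replace the non-inferiority sentence with the improvement or difference question of research question 3.
2. Report the IP-SP difference on the AMP with the 95% confidence interval already planned in SAP 4.1.
3. State that p>0.05 is not evidence of non-inferiority.
4. As a minor clarification, use the term *subscale* at one level throughout, and say whether the t-test is run on the two subscales or the six dimensions. If on the two, give or cite the rule that combines thresholds measured in different units. Either choice is open to the sponsor.

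Keeping the hypothesis with a justified margin and a confidence-limit rule would be the alternative, but step 4 shows that at this sample size only a wide margin would have reasonable power.

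**Cost.** No new data or participants are needed. The permitted AMP claim becomes weaker: a null result could be reported only as an estimate with its interval. The protocol and SAP wording must be amended, and under protocol 2.10 important changes to outcomes or analyses first need approval from the relevant parties.
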